3.2.2 Safety Endpoints

Safety is assessed by the monitoring and recording of adverse events (AEs), clinical laboratory tests, vital signs and physical examination findings.

3.2.3 Endpoint Definitions

- The loss of desensitization is defined as the decline in sensitivity threshold at the final DBPCFC from the 48th month DBPCFC.
- NOAEL is the highest dose observed not to produce any adverse effect and LOAEL is the lowest dose that is observed to produce an adverse effect. Experimentally determined individual's true sensitivity threshold lie between NOAEL and LOAEL. The establishment of individual NOAELs and LOAELs is dependent upon the selection of and spacing between doses selected in the clinical challenge trial design.

4. OVERALL STUDY DESIGN AND PLAN

This is a Phase 2, open label 52-month study designed to evaluate the safety and efficacy of peanut SLIT in inducing clinical desensitization among peanut allergic children.

The study consists of a Screening visit, a Baseline Visit (sometimes combined with the Screening Visit), a build-up phase (approximately, 20 weeks), a Maintenance phase (42 months) and finally, a Sustained Unresponsiveness phase (17 weeks). The total duration of the study, including Screening and the follow-up period, is approximately 225 weeks. We note that all the 24 subjects that have passed the 48 month time point and have been waiting to be administered the 48th month DBPCFC are continuing to dose daily. Because, based on prior evidence, the benefit of continued dosing past 48 months is considered to be negligible on the overall treatment outcome, a slight extension of maintenance phase is considered negligible for such subject.

Following the qualifying entry 1000 mg peanut protein DBPCFC administered at the baseline, subjects will be administered diluted pumps of concentrated peanut protein extract (5000 mcg/ml) based on the build-up dosing scheme to reach an escalated dose of 4000 mcg. Visits for build-up doses will occur prior to changing peanut dilutions or every 4 weeks. Subjects completing the Duke IRB Pro0003579, UNC IRB 11-2301, CoFAR4 who do not pass the 164 week 10 gm DBPCFC may enroll in this study and resume an escalation schedule starting with the 2000 mcg dose in this SLIT (11-2308, TLC) protocol. This defines the build-up phase.

After completing the escalation schedule, subjects will continue to be administered 4000 mcg of peanut SLIT daily at home and will return to the clinical research unit for follow-up visits every 6 months or more frequently for new or significant symptoms. This defines the maintenance phase.

At the 48th month visit, all subjects undergo a 5000 mg peanut protein DBPCFC to verify desensitization, defined as a reaction threshold greater than MCRT (300 mg of peanut protein). At the same visit, subjects are randomized to one of the 17 weeks of SU phase for administration

of the final DBPCFC to assess SU. SU is claimed if the final DBPCFC reaction threshold is greater than or equal to the larger of MCRT and the 48th month DBPCFC sensitivity threshold. Subjects who fail the 48th month DBPCFC, hence not desensitized, will not be administered the final challenge.

4.1 Selection of Study Population

For a complete list of inclusion and exclusion criteria please refer to Protocol SLIT (11-2308, TLC), version 5.0 issued 19-Mar-2014.

4.2 Double Blind Placebo Controlled Food Challenge (DBPCFC)

Protocol DBPCFCs will be administered on the subject at entry, 48 months and weekly during the seventeen-week tolerance phase by a nurse or physician who is blinded to the testing material. The supervising investigator will also be blinded to testing material. Before each challenge, the subject will have a physical exam and peak expiratory flow measurements performed.

The DBPCFC consists of two parts that will be randomly ordered. One part will consist of graded doses of peanut flour and the other of identical graded doses of placebo in the form of oat flour. The doses will be given every 10-20 minutes up to a cumulative dose of 1000 mg (25 mg, 50 mg, 100 mg, 250 mg, 575 mg) during the entry challenge and up to a cumulative dose of 5000 mg (100 mg, 200 mg, 500 mg, 800 mg, 1300 mg, 2100 mg) during the 48th month and final DBPCFC. There will be a minimum 10 minute observation period between doses to monitor for symptoms.

After administration of the first part of the challenge the subject will be observed for a minimum period of 1 hour prior to starting the second part. Reactions will be scored using a Food Challenge Symptom Score (FCSS) sheet. If the subject begins to have significant objective or persistent subjective symptoms, the food challenge will be terminated and the subject will be given appropriate treatment. Subjects who are symptomatic and receive treatment are observed for a minimum of 2 hours after the challenges are completed before being discharged from the clinical research unit.

4.3 Method of Week Assignment for the Final Challenge and Randomization

The following criteria must be satisfied in order for the patient to continue to the SU phase of the study and be randomized:

1. The patient achieves MCRT at the 48th month DBPCFC to continue to the SU phase. This requires patient to be asymptomatic upon administration of 300 mg dose as assessed by Food Challenge Symptom Score sheet.
2. If subjects are found symptomatic and AEs that occur are considered to be intolerable at or below the MCRT, subjects will be refrained from taking the final challenge and will be considered to have lost their desensitization at week 0.
3. No subject will be administered a final challenge dose higher than the NOAEL attained at the 48th month DBPCFC.

Before the start of the SU phase of the study, a computer-generated block randomization schedule is prepared such that each subject has an equal probability of being randomized to one of the weekly challenges held in initial 6 weeks, between 7-12 weeks and between 13-17 weeks. Based on the randomization schedule, three qualified subjects are randomly assigned to one of the final DBPCFC administered each week during the study's 17-week SU phase.

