	
 
• Subjects who are unable to consume > (more than) 300 mg of peanut protein without symptoms will complete the study and not proceed to further evaluations. These subjects will be recommended to resume strict peanut avoidance.
 
• Subjects who are able to consume <math>\geq</math> (greater than or equal to) 300 mg of peanut protein without symptoms will be randomized to withhold study drug and all peanut consumption for a period between 1 and 17 weeks. This avoidance period will be followed by a DBPCFC to assess persistence of the desensitization effect (sustained unresponsiveness).        After this final DBPCFC, the study will be completed and the subject will be recommended to transition to a daily peanut food equivalent.
 

Study Procedures
	
The following procedures will be performed according to the schedule in Appendix 1:
 
 
• Medical and allergy history (including dietary history)
 
• Physical examination
 
• Peak flow rates (if capable)
 
• Serum analysis for peanut-specific immunoglobulins (ImmunoCAP)
 
• Whole blood for basophil activation and T-cell studies
 
• Sublingual Immunotherapy (SLIT)
 
• Double-blind, placebo-controlled, food challenge (DBPCFC) to peanut
 
• Endpoint titration peanut skin prick testing
 
• Saliva collection for immunoglobulin studies
 

Study Stopping Rules
	
 
• Any death related to study drug dosing.
 
• Greater than 2 severe anaphylactic reactions related to study drug dosing at any stage of the protocol.
 
• Greater than 3 subjects who require more than 1 intramuscular epinephrine injection during dose escalation or maintenance dosing of study drug.
 
 
If any of the above occurs, enrollment and uposing will be halted until there's a review by the DSMB, FDA, and IRB.

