### **1.4 Known and Potential Risks and Benefits to Human Participants**

#### **1.4.1 Risks**

The build-up and daily maintenance doses of SLIT may cause allergic symptoms including sneezing, rhinorrhea, urticaria, angioedema, flushing, flares of eczema, ocular, nasal, oral and/or throat pruritus, throat tightness, nausea, vomiting, abdominal discomfort, cough, wheezing, and/or shortness of breath in addition to severe anaphylaxis. The most common symptom associated with SLIT dosing is oropharyngeal itching present in 9.3% of all doses. As of October 24, 2012, no subject in our ongoing SLIT study (NCT# 00597727; UNC IRB 11-2296; Duke Pro00001553) has had dosing-related anaphylaxis requiring treatment with epinephrine [23]. The likelihood of a subject experiencing allergic symptoms will be lessened by starting at small amounts of the peanut protein for dosing per this SLIT protocol.

Double-blind, placebo-controlled food challenges (DBPCFC) may induce an allergic response with symptoms similar to those described for SLIT dosing. The risk of a severe allergic reaction is reduced by conducting the challenge in a monitored clinic setting, initiating the challenge with a very small amount of the food, gradually increasing the dose, and stopping the challenge at the first sign of a reaction. If subjects have an allergic reaction during the challenges, they may need oral, intramuscular, or intravenous medications (subjects will have an IV catheter in place during all DBPCFCs). Trained personnel, including a physician, as well as medications and equipment, will be immediately available to treat any reaction.

Other risks include those related to blood drawing and skin testing. Blood drawing may aggravate a pre-existing anemic condition, but this risk is minimized by restricting the volume drawn to a maximum of 3 ml per kg in accordance with United States Department of Health and Human Services recommendations [28]. Additional risks are those attendant to any needle puncture, including slight bruising, local infection, or the possibility of the subject fainting.

Skin prick tests (not intradermal) will be performed by techniques reflecting general standard of care and cause discomfort (the sensation of a scratch and a pruritic, transient hive may result). Such tests could theoretically induce a systemic allergic reaction, but this is exceedingly rare.

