## STUDY DESIGN

This SLIT study is a prospective, randomized, open-label study based on previous experience at Duke University Medical Center using OIT and SLIT in food allergic subjects. The study will enroll 55 participants with peanut allergy with a goal of 50 children completing protocol interventions. Upon enrollment, all subjects will undergo an entry DBPCFC with 1000 mg of peanut protein to confirm the peanut allergy diagnosis and establish a baseline threshold level. Following a positive DBPCFC, each subject will begin the study drug with peanut SLIT at a starting dose of 1 pump of a 1/100 dilution of peanut concentrate (2500 mcg peanut protein). During the build-up phase which lasts approximately 20 weeks (Table 1), subjects will dose daily and increase the number of pumps every 1-2 weeks as per the dosing schedule. Subjects return to the research unit for observed dosing with each change in peanut SLIT dilution (1/100, 1/10, full concentration) and with every other dose increase on full concentration until the maintenance dose of 16 pumps of full concentration peanut SLIT (4000 mcg peanut protein) is achieved. Subjects will then continue daily administration of the maintenance dose and return every 6 months for follow-up.

After at least 48 months of peanut SLIT study drug, subjects will undergo a second DBPCFC to 5000 mg of peanut protein to assess desensitization.

- Subjects who are not desensitized are those who are not able to consume more than the MCRT without symptoms, which has been defined as 300 mg of peanut protein. Subjects who consume less than 300 mg of peanut protein without symptoms will stop peanut SLIT and conclude the study. These subjects will not undergo any additional study procedures including the remaining protocol DBPCFCs and will be recommended to resume a strict peanut avoidance diet.
- Subjects who are able to consume more than 300 mg of peanut protein will be randomized to an interval between 1 and 17 weeks during which all peanut including peanut SLIT study drug will be discontinued. This period of avoidance will be followed by a third DBPCFC to 5000 mg of peanut protein to evaluate for the loss of the desensitization effect. After this final DBPCFC, the study will be completed for these subjects. At the primary investigators clinical discretion, they will be recommended to transition to a daily peanut food equivalent to maintain the desensitized effect.

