**5.6 Double Blind Placebo Controlled Food Challenge (DBPCFC)**

Protocol DBPCFCs will be conducted on the clinical research unit at entry, after at least 48 months, and after avoidance of peanut SLIT study drug for a randomly selected interval 1 to 17 weeks. Prior

to the food challenge, subjects will be asked to restrict the use of antihistamines (for 5 half-lives of the drug), beta-agonists (12 hours), theophylline (12 hours), and cromolyn (12 hours).

Before each challenge, the subject will have a physical exam and peak expiratory flow measurements performed if the subject is able to reproduce reliable peak expiratory flow measurements prior to the beginning of the challenges.

The DBPCFC consists of 2 parts. A representative from [name] laboratory will randomly determine the order of the 2 parts and prepare all challenge materials. One part will consist of graded doses of peanut flour given every 10-20 minutes up to a cumulative dose of 1000 mg peanut protein (25 mg, 50 mg, 100 mg, 250 mg, 575 mg) during the entry challenge. The 48 month desensitization challenge is 5000 mg (100 mg, 200 mg, 500 mg, 800 mg, 1300 mg, 2100 mg) of peanut protein. The randomly assigned post-avoidance DBPCFC will be identical to the 48 month DBPCFC. The other part of each challenge will consist of identical graded doses of placebo in the form of oat flour.

All food challenges will be administered in a graded fashion to assure safety of subjects. There will be a minimum 10 minute observation period between doses to monitor for symptoms. All food challenges will be performed under physician supervision. The challenge will be administered by a nurse or physician who is blinded to the testing material. The supervising investigator will also be blinded to testing material.

After each challenge the subject will be observed for a minimum period of 1 hour. Reactions will be scored using a Food Challenge Symptom Score sheet. If the subject begins to have clinically significant or persistent subjective symptoms, the food challenge will be terminated and the subject will be given appropriate treatment. Subjects who are symptomatic are observed for a minimum of 2 hours after the challenges are completed before being discharged from the clinical research unit.

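### The month-48 gate to the randomised avoidance phase applies inconsistent symptom standards, so a child with brief symptoms by 300 mg who completes 5000 mg is sent down different paths

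*SAP*

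**What the plan says.** Several passages govern who passes from the month-48 challenge into the randomised avoidance phase.

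- **Synopsis, Study Intervention Description.** Both bullets carry a symptom condition. The second concerns children who consume at least "300 mg of peanut protein without symptoms will be randomized to withhold study drug". Those who fall short finish the study and are advised strict avoidance.
- **Protocol, Study Design, first bullet.** "Subjects who are not desensitized are those who are not able to consume more than the MCRT without symptoms". These children stop SLIT and conclude the study.
- **Protocol, Study Design, second bullet.** "Subjects who are able to consume more than 300 mg of peanut protein will be randomized to an interval". No symptom condition appears.
- **Protocol 5.5 and SAP 4.** Desensitisation is a reaction threshold above 300 mg. Neither place says what counts as a reaction. Protocol 5.5 then randomises every desensitised child.
- **SAP 4.3 item 1.** "This requires patient to be asymptomatic upon administration of 300 mg dose as assessed by Food Challenge Symptom Score sheet".
- **SAP 4.3 item 2.** The final challenge is withheld and loss is dated to week 0 under this condition: "If subjects are found symptomatic and AEs that occur are considered to be intolerable at or below the MCRT".

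The rule for stopping the challenge uses another standard. Protocol 5.6 says "If the subject begins to have clinically significant or persistent subjective symptoms, the food challenge will be terminated". SAP 4.2 is similar, naming significant objective or persistent subjective symptoms.

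**The concern.** The gate and the stopping rule do not use the same symptom standard, and the statements of the gate do not agree with each other. A child can have a symptom that breaks the strict form of the gate but does not stop the challenge, and can then eat the full 5000 mg.

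Three things depend on how that child is handled: whether SLIT stops and strict avoidance is advised or the child is randomised; whether the child belongs to the population that SAP 7 makes primary for efficacy, which consists of randomised patients; and what value the child contributes to the time-to-loss analysis. SAP 10.1 estimates time to loss separately within each month-48 dose interval, and SAP 4.3 assigns three children per week, so the cells are small and a few differently classified children could matter.

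**Working it through.** **Where 300 mg falls.** Protocol 5.6 and SAP 4.2 list steps of 100, 200, 500, 800, 1300 and 2100 mg. The running totals are 100, 300, 800, 1600, 2900 and 5000 mg, which reproduces the stated total of 5000 mg. The 300 mg mark is reached at the end of the second step, so only symptoms at the first two steps matter here. A symptom that first appears later creates no conflict.

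**Test case.** A child has a brief subjective symptom, such as mouth itch, at the 100 or 200 mg step. It is neither clinically significant nor persistent, so the challenge continues, and the child completes 5000 mg.

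| Place | Test applied | Result for this child |
|---|---|---|
| Synopsis, both bullets | 300 mg free of symptoms | Ends the study, avoidance advised |
| Study Design, bullet 1 | More than 300 mg free of symptoms | Not desensitised, SLIT stops, study ends |
| Study Design, bullet 2 | More than 300 mg consumed | Randomised |
| Protocol 5.5, SAP 4 | Reaction threshold above 300 mg | Depends on the undefined word reaction |
| SAP 4.3 item 1 | Asymptomatic at 300 mg | Fails |
| SAP 4.3 item 2 | Symptomatic and intolerable | Not met unless judged intolerable |

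The two Study Design bullets give opposite results. The two SAP 4.3 items are not complements: the child fails the first without meeting the second.

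**The analysis on the strict reading.** SAP 3.2.3 defines the NOAEL as the highest dose without any adverse effect.

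- Symptom at the first step: NOAEL 0, LOAEL 100 mg.
- Symptom at the second step: NOAEL 100 mg, LOAEL 200 mg on the listed doses.

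Both NOAELs are below 300 mg, so SAP 10.1 sets X = 0, immediate loss. SAP 8.1.2 reaches the same result through the LOAEL for a child not given the final challenge. One detail needs care: counted cumulatively, the second-step LOAEL is 300 mg, which is not below 300 mg. The 8.1.2 rule would then not apply although the 10.1 rule still would.

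**The analysis on the objective-reaction reading.** The threshold part of SAP 10.1 right-censors anyone without an objective reaction at the largest dose and sets the NOAEL to that dose. The same child then has the highest threshold the challenge can record, and no ground remains for X = 0.

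**Number affected.** The documents give no rate of non-stopping symptoms at the challenge, so no count can be derived.

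**The case against.** The strongest reply is that the explicit statements mostly agree. The synopsis, the first Study Design bullet and SAP 4.3 item 1 all require freedom from symptoms. The second Study Design bullet sits directly beneath the first and may simply be shorthand. The symptom score sheet named in item 1 is not reproduced and may define what asymptomatic means. This has force: the shorthand reading would remove the conflict within Study Design. It would not explain why SAP 4.3 item 2 adds intolerability, why the threshold model counts only objective reactions, or what a reaction is in Protocol 5.5 and SAP 4. No passage ranks these texts or gives a cut-off on the sheet.

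A reader might infer three stronger things that the documents do not support.

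- *That this child belongs to no SAP category.* On the strict reading SAP 3.2.3, 8.1.2 and 10.1 supply X = 0. The gap lies between the two items of SAP 4.3, not across the whole SAP.
- *That SAP 4.3 both bars and admits the child.* Its lead-in makes the criteria conditions for randomisation, so failing item 1 already bars entry. Item 2 attaches a consequence to a subset and does not admit anyone.
- *That the number of children can be calculated.* Protocol 1.4.1 says "The most common symptom associated with SLIT dosing is oropharyngeal itching present in 9.3% of all doses". That rate is per sublingual dose in micrograms, not per 100 or 200 mg challenge step after at least 48 months of treatment. Applied to 45 children, it gives 45 × [1 − (1 − 0.093)²] = 8.0 if the two steps are independent, and 45 × 0.093 = 4.2 if they are fully dependent within a child. The answer is set by the assumption. Protocol 5.2 also describes the 45 as eligible for randomisation, so it is not clearly the number challenged.

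Passages elsewhere that treat oral itch as minor during SLIT dosing do not settle the matter, because they do not concern the challenge.

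**Conclusion.** The point holds as an inconsistency that should be resolved. A child with transient symptoms at or below cumulative 300 mg who completes 5000 mg ends the study under the synopsis and the first Study Design bullet, is randomised under the second, and fails SAP 4.3 item 1 without meeting item 2. For that child the difference in the analysis is as large as it can be: X = 0 for time to loss on the strict reading, against right-censoring at the top dose in the threshold model.

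This rests on the challenge continuing through brief symptoms, which both stopping rules allow, and, for the right-censoring result, on the symptom being subjective. It does not rest on any symptom rate. How many children are affected is unknown. The mismatch between more than 300 mg and at least 300 mg is a separate matter.

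**What to change.** The investigators should reconcile these passages to one symptom criterion. Which criterion applies is theirs to decide.

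1. Use the same wording in both synopsis bullets, both Study Design bullets, Protocol 5.5, SAP 4 and SAP 4.3 item 1.
2. Rewrite SAP 4.3 item 2 as the exact complement of item 1, so that every challenged child is either eligible for randomisation or a week-0 loss.
3. Align the X = 0 rules in SAP 8.1.2 and 10.1 with that criterion, and say whether the dose levels they use are single or cumulative.
4. State how the criterion relates to the stopping rule in Protocol 5.6 and SAP 4.2.
5. Tabulate children with non-stopping symptoms at or below cumulative 300 mg by the path they took.

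The cost is protocol and SAP wording plus one table. Reactions are already scored on the symptom score sheet. SAP 1 reports 24 children past 48 months and still awaiting this challenge, so the wording is best settled before they are challenged.

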***Sustained Unresponsiveness Assessment by DBPCFC***

All subjects who are desensitized after at least 48 months will be randomized to an interval between 1 and 17 weeks during which all peanut including peanut SLIT study drug will be discontinued. This period of avoidance will be followed by a third DBPCFC to 5000 mg of peanut protein to evaluate for the loss of the desensitization effect.

- At the completion of the study, subjects will be given the option to transition to a daily peanut food equivalent versus resuming a strict peanut avoidance diet.

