1. BACKGROUND

This Statistical Analysis Plan (SAP) has been written to address the concerns identified in the March 19, 2014 protocol abbreviated Peanut SLIT and Tolerance (UNC IRB#11-2308), which included our proposed primary analysis plan aimed at assessing effectiveness of peanut SLIT to induce clinical tolerance 6 months after its discontinuation.

We recognize the investigating team's concerns regarding the assumption that patients will be able to clear the food challenge administered after 6 months of SLIT discontinuation to demonstrate clinical tolerance. The team believes this assumption is rather optimistic, less supported by prior research and suspects that the current study protocol calls for negligible success rate by the end of 6 months of SLIT discontinuation as most of the subjects would fail for clinical tolerance. Since time to loss of desensitization (TLD) is an important dimension that, in our knowledge, no prior study has investigated, provides clinically valuable information and helps facilitate future study design, this study provides an opportunity and a robust framework to study the same. As a result, the revised protocol analyzes a systematic approach to address this concern. We believe that with few changes in the study design and efficacy analysis plan, the revised protocol will help address new objectives of primary enquiry and will provide greater precision to cater to individual's need.

With 51 total enrollees, we are midway through the study's conduct with 24 subjects clearing 48 months of dose maintenance period and waiting to be administered the 48th month food challenge and to be randomized to the placebo or the treatment arm as per the existing protocol. The revised study design calls for amendments beyond the 48 months' period of dose maintenance to include 48th month food challenge followed by discontinuation of SLIT for all subjects for at most 17 weeks, dissolving the need for a two-arm trial. Subjects will be randomized to weekly observed time points during 17 weeks following the 48th month food challenge when the final food challenge will be administered to assess individual's persistent desensitization also known as sustained unresponsiveness (SU). The structure of this final food challenge will be similar to that of the earlier (48th month) food challenge with similar levels of administered drug doses.

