3.2 Study Endpoints

3.2.1 Efficacy Endpoints

The primary efficacy endpoints are:

- An estimate of the dose as assessed by the 48th month DBPCFC, also called population sensitization threshold, predicted to provoke reactions in 5% and 10% of the peanut-allergic population. This will also give population level NOAEL and LOAEL that would define interval of consecutive administered dose levels within which the population sensitization threshold lies.
- Multiplicative or differential change in the population sensitization threshold as assessed by the 48th month DBPCFC with a unit change in covariates.
- An estimate of time to loss of desensitization for the following events:
 - Subject's true sensitivity threshold to reduce by half, also called half-life of sensitivity threshold.
 - Subject's true sensitivity threshold to maintain at the same level of LOAEL.
 - Subject's true sensitivity threshold to drop by at least one level of LOAEL.
 - Subject's true sensitivity threshold to remain at or above MCRT.
- Estimates of the proportion of patients at a fixed time for any of the above events that define loss of desensitization (bullet 2).
- Multiplicative change in hazard of loss of desensitization with a unit change in covariates.

Secondary efficacy endpoints include:

- Comparative estimates of changes in immune parameters over time among subjects who were induced with clinical desensitization versus those who failed.

- Incidence of all serious adverse events (SAEs) during the study.

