8.1.1 Statistical Assumptions

Time to Loss of Desensitization (TLD) requires more rigorous mathematical framework of stochastic process. However, a good approximation could be achieved using Interval Censoring framework for the latter three events defined in section 3.2.1 (bullet 3). The framework uses following assumptions:

- Desensitization is monotonically decreasing with time. $NOAEL(\text{final DBPCFC}) \leq NOAEL(48\text{th month DBPCFC})$
- Subject's true sensitivity threshold at the 48th month DBPCFC is approximated by his/her NOAEL.
- Subjects with the final DBPCFC NOAEL higher than the 48th month DBPCFC NOAEL will be regarded as exceptions. Their final DBPCFC NOAEL will be considered equal to the 48th month DBPCFC NOAEL for conservative time to loss of desensitization estimates.
- Subjects with 48th month LOAEL < MCRT will also fail at LOAEL administered at the final DBPCFC that are less than MCRT, thereby un-necessitating the need for the final DBPCFC.
- Since the final DBPCFC observation times are randomized, subject's unobserved time to loss of desensitization and the baseline covariates are independent of his/her final DBPCFC observation time.

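### SAP 4.3 caps the final challenge at the child's 48-month NOAEL, while the protocol and SAP 4.2 give the full ladder to 5000 mg; under the cap an unchanged LOAEL is assumed, not measured

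*SAP*

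**What the plan says.** **The cap.** SAP 4.3, third criterion: "No subject will be administered a final challenge dose higher than the NOAEL attained at the 48th month DBPCFC".

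**The full ladder, in the protocol.** Section 5.6 sets the doses: "The 48 month desensitization challenge is 5000 mg (100 mg, 200 mg, 500 mg, 800 mg, 1300 mg, 2100 mg) of peanut protein". It then says of the final challenge: "The randomly assigned post-avoidance DBPCFC will be identical to the 48 month DBPCFC". Section 5.5, under Sustained Unresponsiveness Assessment, says: "This period of avoidance will be followed by a third DBPCFC to 5000 mg of peanut protein to evaluate for the loss of the desensitization". The Study Design section gives the same 5000 mg.

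**The full ladder, in the SAP itself.** SAP 4.2 describes, with no cap, dosing at both later challenges: "up to a cumulative dose of 5000 mg (100 mg, 200 mg, 500 mg, 800 mg, 1300 mg, 2100 mg) during the 48th month and" (the sentence ends by naming the last challenge). SAP 1 says: "The structure of this final food challenge will be similar to that of the earlier (48th month) food challenge with similar levels of administered drug". SAP 8.1.1 adds: "Subjects with the final DBPCFC NOAEL higher than the 48th month DBPCFC NOAEL will be regarded as exceptions", and recodes their final NOAEL down to the 48-month value.

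**The endpoint concerned.** Among the primary time-to-loss events in SAP 3.2.1 and protocol 2.2.1 is: "Subject's true sensitivity threshold to maintain at the same level of LOAEL". A fall of one LOAEL level or more is listed as a separate event.

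**The concern.** Both rules cannot be followed for a child who reacted during the 48-month challenge. That child's 48-month LOAEL lies one step above the NOAEL, so the cap withholds exactly the dose that provoked the earlier reaction, and the protocol includes it. The inconsistency is not only between the two documents: SAP 4.3 also disagrees with SAP 1, 4.2 and 8.1.1.

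Two things are at stake. One is the maximum peanut exposure of children who are off treatment. The other is what the final challenge can show. If dosing stops at the 48-month NOAEL and the child does not react, nobody learns whether the LOAEL is unchanged or has risen.

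**Working it through.** **1. The stated total.** The steps in protocol 5.6 and SAP 4.2 sum to 100 + 200 + 500 + 800 + 1300 + 2100 = 5000 mg, as stated. Cumulative doses are 100, 300, 800, 1600, 2900 and 5000 mg.

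**2. Ceilings under each rule.** The cap is read as stopping at the step that was the 48-month NOAEL.

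| 48-month NOAEL, step (cumulative), mg | Ceiling, SAP 4.3 | Ceiling, protocol | Not given under the cap | Ratio |
|---|---|---|---|---|
| 200 (300) | 300 | 5000 | 4700 | 5000/300 = 16.7 |
| 500 (800) | 800 | 5000 | 4200 | 5000/800 = 6.25 |
| 800 (1600) | 1600 | 5000 | 3400 | 5000/1600 = 3.1 |
| 1300 (2900) | 2900 | 5000 | 2100 | 5000/2900 = 1.7 |
| 2100 (5000) | 5000 | 5000 | 0 | 1 |

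The first row applies only if tolerating exactly 300 mg qualifies for randomisation. The synopsis (second bullet) and SAP 4.3 allow it; the Study Design section and protocol 5.5 require more than 300 mg. On the stricter reading the largest ratio is 6.25.

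**3. What each rule lets the analysis see.** Take the five 48-month NOAEL levels in the table and seven possible final outcomes (reaction at the first step, up to tolerance of all six): 5 × 7 = 35 pairs. Under the full ladder the final NOAEL is what it is. Under the cap it is the smaller of that value and the 48-month NOAEL.

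| Quantity | Pairs that differ between rules |
|---|---|
| Fall of one LOAEL level or more | 0 |
| Threshold halved, NOAEL as proxy | 0 |
| Below the MCRT (300 mg) | 0 |
| Same LOAEL level, before the SAP 8.1.1 recoding | 4 + 3 + 2 + 1 = 10 |
| Same LOAEL level, after the recoding | 0 |
| Final LOAEL measured under the full ladder, unmeasured under the cap | 4 + 3 + 2 + 1 = 10 |

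The zeros follow directly. Each loss event needs a reaction at or below the 48-month NOAEL, and those doses are given under both rules. The fourth row counts final outcomes above the 48-month level, which the cap records as equal to it. The last row counts outcomes at or above the 48-month level that still end in a reaction on the full ladder. Under the stricter entry rule there are 4 × 7 = 28 pairs, and both counts of 10 become 3 + 2 + 1 = 6. These are counts of possible outcomes, not of children.

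**4. The likelihood.** SAP 10.1 uses only the challenge week T and the indicator that loss occurred by T. A child without loss contributes 1 − F(T) under either rule.

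**5. Text that changes meaning.** The SAP 8.1.1 rule for a raised final NOAEL has no cases under the cap. SAP 8.1.2 treats tolerance of the highest administered dose as a LOAEL beyond the observed time. Under the cap that dose would be the child's own ceiling; under the full ladder it is the 2100 mg step.

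**The case against.** The strongest reply is that the planned primary analysis does not change. SAP 8.1.1 takes NOAEL as the threshold, assumes it cannot rise, and recodes any rise to no change, so the extra information from the full ladder would be discarded. Step 3 confirms this, and the point stands.

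Three stronger readings are therefore tempting but unsupported:

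- **That the cap makes the LOAEL endpoints unobservable.** A fall of one level or more is fully observable under the cap. Only constancy is not directly seen, and only in a capped child who does not react.
- **That the cap causes maintained children to be right-censored.** They are right-censored at T under either rule.
- **That the half-life analysis is damaged.** SAP 8.1.1 keeps half-life outside the interval-censoring framework, and SAP 10.1 defers it to a later double-censoring analysis without a stated likelihood. The final LOAEL might matter there, but the documents do not allow that to be shown. Nor is a check of monotonicity among the planned analyses; SAP 10.1 validates only the exponential form.

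It can also be said that staff follow the protocol. SAP 2 refers readers there for conduct and names protocol version 5.0 of March 2014, while the present protocol mentions February 2016, so version lag is a plausible explanation. That makes it uncertain that different doses would actually be given. It does not remove the contradiction: the SAP criterion is worded as a rule of conduct, and SAP 4.2 disagrees with it.

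**Conclusion.** The contradiction is plain on the page and should be resolved. It affects every randomised child who reacted during the 48-month challenge; how many that is cannot be known from the documents.

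The ratios of 1.7 to 6.25, or 16.7 under the looser entry reading, are ceilings. Challenges stop on symptoms, so the dose actually delivered differs only for a capped child who again tolerates everything up to the 48-month NOAEL.

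The statistical consequence is narrower than the dosing conflict. The loss indicators and the case-1 likelihood are unaffected. What depends on the choice is whether threshold constancy and the absence of rises are measured or assumed. This conclusion rests on the SAP's use of NOAEL as the threshold and on reading the cap by dose step.

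**What to change.** Before the first final challenge, reconcile SAP 4.3 (third criterion) with the protocol's Study Design, 5.5 and 5.6 and with SAP 1 and 4.2. Which rule applies is for the sponsor and investigators to decide. Then align the analysis text.

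- **If the cap is retained:** amend the protocol sections, SAP 1 and SAP 4.2 to state it. Remove the SAP 8.1.1 rule for raised final NOAELs. Say in SAP 3.2.1 that maintenance means no reaction at or below the 48-month NOAEL. Say in SAP 8.1.2 that the highest administered dose is the child's own capped dose.
- **If the full ladder is retained:** remove the third criterion from SAP 4.3. Record and report the observed final NOAEL and LOAEL, including any rises, as a check on the monotonicity assumption.

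Settle at the same time whether tolerating exactly 300 mg qualifies for randomisation, since the largest difference in ceiling depends on it. The cost is one decision and a few text edits. Neither route needs new assessments or a change to the case-1 likelihood.
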